2.4.1.4 Related Adverse Events

For each type of causality (NVDX3, grafting surgery, other study procedure) an adverse event is considered related if it is assessed as possibly, probably or definitely related or if the assessment is missing.

An adverse event will be considered NVDX3-related only in case the causality is NVDX3. It is not NVDX3-related if the cause is the grafting surgery or other study procedure.

2.4.1.5 Adverse Events of Special Interest (AESI)

The following adverse events will be considered as of special interest:

- Hypersensitivity reaction
- Immunological reaction
- An AE requiring immunosuppressive medication
- Ectopic bone formation
- Tumor formation
- Continued non-union/Non-fusion
- Refracture of the targeted area
- Revision surgery/intervention including removal of NVD-X3
- Any other condition considered by the treating physician as treatment failure

A reportable AESI (rAESI) is defined as an AESI that is assessed by the Principal Investigator as possibly, probably or definitely related to NVDX3.

2.4.1.6 Expectedness of Adverse Events

Each AE is assessed as expected or unexpected, in the light of the reference safety information (RSI) included in the latest version of the approved Investigator Brochure.

2.4.2 Safety Assessment by Local Radiologist

[REDACTED]

2.4.3 Laboratory Data

At Screening, HD, at 2 and 6 weeks and at 3, 6 and 12 months post-IS the following information is collected (at 3, 6 and 12 months post-IS: only upon occurrence or any suspicion of safety related issues):

2.4.3.1 Biochemistry

- [REDACTED]

2.4.3.2 Hematology

- [REDACTED]

2.4.3.3 Coagulation

- [REDACTED]

2.4.3.4 Serology (only at Screening)

- [REDACTED]

2.4.4 Vital Signs

At Screening, IS, HD, at 2 and 6 weeks and at 3, 6 and 12 months post-IS the following information is collected:

- Height (cm) (only at screening)
- Weight (kg)
- BMI (kg/m²)
- Body temperature (°C)
- Pulse rate (beats/min)
- Respiratory rate (breaths/min)
- Mean systolic blood pressure (mmHg)
- Mean diastolic blood pressure (mmHg)

2.4.5 Physical Examination

At Screening, IS, HD, at 2 and 6 weeks and at 3, 6 and 12 months post-IS the following information is collected:

- [REDACTED]

2.4.6 Triplicate 12-Lead ECG

At IS and at 12 months post-IS the following information is collected:

2.4.7 Pregnancy Test

At Screening and at 12 months post-IS the following information is collected:

2.5 Concomitant Treatments

2.5.1 Concomitant Medications

The following information on concomitant medications is collected:

Concomitant medications will be coded

2.5.2 Concomitant Therapy

The following information on concomitant therapies is collected:

2.6 Course of the Study

2.6.1 Study Dates

- Date of written informed consent
- Date of each visit

2.6.2 End of Study

-
- Date of study termination

- Primary reason for premature discontinuation (Withdrawal by patient, Adverse event, Protocol deviation, Study terminated by sponsor, Lost to follow-up, Death, Physician decision, Screen failure, Other), when applicable
- Date of death, when applicable

[REDACTED]

[REDACTED] – [REDACTED]

[REDACTED]

3 Statistical Methodology

3.1 Statistical Software

The SAS Version 9.4 statistical software package will be used for all statistical analyses.

3.2 Analysis Sets

The following analysis sets will be considered for the analysis:

Safety Set (SAF)

All patients treated with NVDX3.

Modified Full Analysis Set (mFAS)

All patients satisfying all inclusion criteria and none of the exclusion criteria and for whom any efficacy assessment is available.

The analysis sets will be determined by a review of the data prior to database lock.

The analysis of the demographic data and other baseline characteristics will be performed for both the SAF and the mFAS.

The analysis of efficacy will be performed on the mFAS.

The analysis of safety and concomitant treatments will be performed on the SAF.

3.3 Missing Data

No imputation strategies will be applied unless specified otherwise.

3.4 Summary Statistics

Unless specified otherwise, the following summary statistics will be used to describe the data:

- For quantitative variables: mean, 95% confidence interval (CI) on the mean, standard deviation (SD), minimum, 1st quartile, median, 3rd quartile, range, maximum, number of available and number of missing observations.
- For categorical variables: number and percentage for each of the scores or categories, and the number of observations.

3.5 Definition of Baseline

For the statistical analysis of change versus baseline for the efficacy endpoints the baseline is defined as the data collected at hospital discharge (HD)⁵ except for the Numerical Rating Scale for pain where the observation at the screening visit will be used as the baseline.

⁵ The baseline timepoint for radiological assessment on X-ray has been changed compared to the protocol, as detailed in Section 3.6.

3.6 Changes with Respect to the Analysis Foreseen in the Protocol

- With respect to the statistical analysis of adverse events the table showing frequency distributions and total number of events for patients with any SAE by MedDRA SOC and by MedDRA SOC and PT, and maximal severity will not be provided.
- For safety assessment, TEAEs will be described after the implant surgery, as per definition of treatment-emergent AEs. The assessment period between screening and week 6 post-IS (V5 included) indicated in the protocol for the acute events was erroneous and will be replaced by the assessment period between IS and week 6 post-IS (V5 included).
- For physical examination, the following additional data is recorded with respect to skin inspection of the affected arm:
 - Scar (Normal, Abnormal)
 - Open wound (Absent, Present)
 - Ulceration (Absent, Present)
 - Injury median nerve (Absent, Present)
- With respect to the radiological assessment on X-ray based on the eLSS tool the protocol mentions peri-operative X-ray acquisition as the baseline. However, instead of X-ray, fluoroscopic images were taken during surgery, which could not be used as baseline, because there was not guaranteed standardization regarding positioning and magnification. As a solution the X-ray acquired at Hospital Discharge (HD) is used as baseline for the eLSS assessments. It is confirmed by the principal central radiologist that this change does not impact the bone fusion scoring, as the image is acquired in the immediate post-operative period within days from surgery and considering the fact that bone fusion typically takes weeks to begin to be visualized by medical imaging. Furthermore, the protocol foresaw a central review of both CT and X-ray at Hospital Discharge (HD) but these assessments were not done since it is assumed that eLSS = 0 at baseline. As a consequence eLSS values were considered 0 at baseline defined as HD.
- Peri-operative measurements allowed to be performed on X-ray images acquired at hospital discharge, when quality fluoroscopy not sufficient.
- “Mid-term follow-up” will replace “long-term follow-up” in the core study NVDX3-CLN01 to differentiate this time period from that of the long-term follow-up study, NVDX3-CLN0X.

4 Details of the statistical analysis

4.1 Patient Characteristics

Summary statistics for demographic data and other baseline characteristics will be provided for the SAF and the mFAS.

4.1.1 Demographic Data

Descriptive statistics will be provided for:

- Approximate age at screening (years)

Frequency distributions will be provided for:

- Sex
- Race
- Childbearing potential status

4.1.2 Contraception Data

These data will be listed only

4.1.3 Smoking History

Frequency distributions will be provided for:

- Has the patient ever used tobacco?

Descriptive statistics will be provided for:

- Average daily cigarette count in the recent 12 months
- Duration of tobacco use (days)

4.1.4 Employment Data

These data will be listed only.

4.1.5 Index Fracture Classification

These data will be listed only.

4.1.6 Medical History

These data will be listed only.

4.2 Study Treatment

4.2.1 Implant Surgery

These data will be listed only.

4.2.2 Drug Accountability

Frequency distributions will be provided for estimated reconstituted volume used.

All other data will be listed only.

4.3 Efficacy Analysis

The analysis of all efficacy data will be performed on the mFAS.

4.3.1 Central radiological assessment of CT using eLSS

For the statistical analysis of eLSS data including bone formation, bone modeling and bone union as well as the eLSS total score, [REDACTED]

Frequency distributions will be provided at each scheduled visit for each of the following variables:

- Bone formation
- Bone remodeling
- Bone union

For the Total eLSS score descriptive statistics will be provided at each post HD visit.

Frequency distribution will be provided for the continued non-union at 12 months post-IS.

A profile plot will be provided for eLSS total score as well as a box plot showing eLSS total score at all post-IS visits.

A scatter plot presenting eLSS total score as assessed by the first reader versus second reader and a Bland-Altman plot will be created for the agreement between both readers. For both graphs, different symbols will be used for each visit on which the assessments are made.

Data from the both readers will be listed.

The following data will be listed only:

- Position and volume NVDX3
- Position and integrity of fixation devices
- Is the radius well aligned

4.3.2 Central radiological assessment of X-Ray using eLSS

For the statistical analysis of eLSS data including bone formation, bone modeling and bone union as well as the eLSS total score, [REDACTED]

Frequency distributions will be provided at each scheduled visit for each of the following variables:

- Bone formation
- Bone remodeling
- Bone union

For the Total eLSS score descriptive statistics will be provided at each post HD visit.

Frequency distribution will be provided for the continued non-union at 12 months post-IS.

A profile plot will be provided for eLSS total score as well as a box plot showing eLSS total score at all post-IS visits.

A scatter plot presenting eLSS total score as assessed by the first reader versus second reader and a Bland-Altman plot will be created for the agreement between both readers. For both graphs, different symbols will be used for each visit on which the assessments are made.

Data from the both readers will be listed.

The following data will be listed only:

- Position and volume NVDX3
- Position and integrity of fixation devices
- Is the radius well aligned

All peri-operative measurements will be listed only.

4.3.3 Clinical Assessments

4.3.3.1 Grip Strength Test

Descriptive statistics will be provided at each visit for the actual value and change versus baseline (HD) for the difference from normal.

The individual scores for each arm will be listed.

4.3.3.2 Physician reported Modified Mayo Wrist Score

Frequency distributions will be provided at each scheduled visit for each of the following variables:

- Pain
- Satisfaction
- Range of motion
- Grip Strength

Descriptive statistics will be provided at each visit for the total score.

Frequency distributions will be provided at each scheduled visit and shift tables between baseline (HD) and each post-baseline visit for the final result.

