#### 7.1.2. Physician reported Modified Mayo Wrist Score

The Modified Mayo Wrist Score (MMWS) is a modification of the Geen and O'Brien score (Appendix 4). There is a total of 100 points which are divided among the evaluator's assessment of pain (25 points), active flexion/extension arc as a percentage of the opposite side (25 points), grip strength as a percentage of the opposite side (25 points), and the ability to return to regular employment or activities (25 points).

Pain is rated as none (25 points), mild (20 points), moderate (10 points), or severe (0 points) by the evaluator, based on the patient's subjective description.

The total score ranges from 0 to 100 points with higher scores indicating a better result. An excellent result is defined as 90–100 points, good is 80–89, fair is 65–79 points, and poor is less than 65 points.

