## APPENDIX 4: Modified Mayo Wrist Score (MMWS)

Category	Score	Findings
Pain (25 points)	25	No pain
	20	Mild pain with vigorous activities
	20	Pain only with weather changes
	15	Moderate pain with vigorous activities
	10	Mild pain with activities of daily living
	5	Moderate pain with activities of daily living
Satisfaction (25 points)	0	Pain at rest
	25	Very satisfied
	20	Moderately satisfied
	10	No satisfied, but working
	0	No satisfied, unable to work
	25	100% percentage of normal
Range of motion (25 points)	15	75% - 99% percentage of normal
	10	50% - 74% percentage of normal
	5	25% - 49% percentage of normal
	0	0% - 24% percentage of normal
	25	100% percentage of normal
	15	75% - 99% percentage of normal
Grip strength (25 points)	10	50% - 74% percentage of normal
	5	25% - 49% percentage of normal
	0	0% - 24% percentage of normal
	90 - 100	Excellent
	80 - 89	Good
	65 - 79	Fair
Final result (total points)	<65	Poor

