1.3.2.2 Efficacy

Radiological assessments on Computed Tomography data (CT) using the extended Lane and Sandhu Scoring tool (eLSS)

The following assessments will be performed at 3 and 12 months post-IS.

- Evaluation of bone formation status
- Evaluation of bone union status
- Evaluation of bone remodeling status
- Evaluation of Total extended Lane and Sandhu Score

Assessments will be compared to HD.

Radiological assessments on X-ray Using the eLSS tool

The following assessments will be performed at 2 and 6 weeks and at 3, 6 and 12 months post-IS according to standard of care.

- Evaluation of bone formation status
- Evaluation of bone union status
- Evaluation of bone remodeling status
- Evaluation of Total extended Lane and Sandhu Score

Assessments will be compared to HD³.

² The assessment period for the acute events has been changed compared to the protocol, as detailed in Section 3.6.

³ The baseline timepoint has been changed compared to the protocol, as detailed in Section 3.6.

Clinical assessments

The following assessments will be performed at HD, at 2 and 6 weeks and at 3, 6, and 12 months post-IS:

- Grip strength measure with a hydraulic hand dynamometer
- Modified Mayo Wrist Score (MMWS): A physician-based scoring evaluating the patients' pain, active flexion/extension arc, grip strength and ability to return to regular employment or activities.
- PRWE Questionnaire: A patient reported scoring evaluating the patients' wrist pain and disability.

The post-HD assessments will be compared to HD.

Numeric Rating Scale (NRS) for pain, a patient reported scoring evaluating the patients' pain, will be performed at screening, at HD and 2 and 6 weeks, 3, 6, and 12 months post-IS.

The post-screening assessments will be compared to screening.

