4.3.3.3 Numerical Rating Scale for Pain

Descriptive statistics will be provided at each visit for the actual value and change versus baseline (Screening) for the numerical rating scale for pain.

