4.3.3.4 Patient-Rated Wrist Evaluation

Descriptive statistics will be provided at each visit for the actual value and change versus baseline (HD) for the following variables:

- Total pain score
- Total function score
- Total score

All subscores for pain and function will be listed.

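### The MMWS total score has no planned change from hospital discharge, unlike grip strength, NRS pain and PRWE; the only named comparison is a category shift table that can hide gains of up to 60 points

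*SAP*

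**What the plan says.** SAP 1.3.2.2 lists grip strength, MMWS and PRWE as clinical assessments at HD and at each later visit, and states: "The post-HD assessments will be compared to HD". SAP 3.5 defines HD as the baseline for change in the efficacy endpoints, with NRS pain (baseline at screening) as the exception.

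The four clinical measures are then handled as follows:

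- **Grip strength (SAP 4.3.3.1):** "actual value and change versus baseline (HD) for the difference from normal".
- **NRS pain (SAP 4.3.3.3):** "actual value and change versus baseline (Screening) for the numerical rating scale for pain".
- **PRWE (SAP 4.3.3.4):** "Descriptive statistics will be provided at each visit for the actual value and change versus baseline (HD) for the following variables", namely pain, function and total score.
- **MMWS (SAP 4.3.3.2):** frequencies of the four components by visit; for the total, "Descriptive statistics will be provided at each visit for the total score"; for the final category, frequencies by visit and "shift tables between baseline (HD) and each post-baseline visit for the final result".

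Protocol 7.1.2 and Appendix 4 set the same result categories on the 0 to 100 total: Excellent 90–100, Good 80–89, Fair 65–79, and "poor is less than 65 points".

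**The concern.** MMWS is the only one of the four clinical measures whose numerical score has no planned change from baseline. SAP 3.6, which lists departures from the protocol, gives no reason for treating it differently.

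The comparison that is planned uses four categories, and the lowest covers everything from 0 to below 65. A patient soon after plating of a C2 or C3 fracture may well start low on motion and grip, and can then improve a good deal without leaving Poor. If most patients start in Poor, the shift table has one populated starting row and tells the reader what the follow-up frequency table already says. The size and spread of within-patient improvement would then not be reported for this score. In a single-arm study of 10 patients, that is the most direct description of a patient's evolution.

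**Working it through.** **Inputs.** From Protocol Appendix 4:

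- Pain: 25, 20, 20, 15, 10, 5 or 0 (seven rows).
- Satisfaction: 25, 20, 10 or 0 (four rows).
- Motion and grip, each: 25, 15, 10, 5 or 0. The band "25% - 49% percentage of normal" scores 5, and 0–24% scores 0.
- Poor: total below 65.

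The sample size is 10 (SAP 1.4). Appendix 4 is the relevant table because SAP 4.3.3.2 analyses its four components, satisfaction included. Protocol 7.1.2 describes the components differently (return to work instead of satisfaction, and other pain steps). It gives the same 25-point maxima and the same Poor cut-off, but no bands for motion or grip, so the ceiling below rests on Appendix 4.

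**Step 1: ceiling with motion and grip both below 50%.**
Maximum total = 25 + 25 + 5 + 5 = 60 < 65. There are 7 × 4 × 2 × 2 = 112 row combinations in this state. All 112 are Poor, with totals from 0 to 60 in steps of 5 (13 possible values).

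**Step 2: what the shift table can hide.**
All component scores are multiples of 5, so the highest Poor total is 60. A patient going from 0 to 60 gains 60 points and is shown as Poor to Poor.

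**Step 3: how far this extends beyond the 50% threshold.**
- One measure at 50–74% and the other at 0–24%: maximum 25 + 25 + 10 + 0 = 60, still Poor.
- Both measures below 75%: only five point combinations (pain, satisfaction, motion, grip) reach 65. They are (25, 25, 10, 10) = 70 and, each totalling 65, (25, 25, 10, 5), (25, 25, 5, 10), (25, 20, 10, 10) and (20, 25, 10, 10).
- Pain score 10 or less and satisfaction 20 or less: motion plus grip must supply at least 65 − 30 = 35. Since 15 + 15 = 30 is not enough, one of the two must be at 100% of normal.

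These are counts of score combinations. They show what the scale permits, not how often patients fall there.

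**Step 4: how many patients might start as Poor.**
The documents give no HD values, so let q be the assumed proportion of patients with motion and grip both below 50% at HD. All of them are Poor, and others may be too, so the figures are lower bounds. Expected number Poor ≥ 10q. The probability of at least 9 of 10 Poor is at least 10q⁹(1 − q) + q¹⁰.

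| Assumed q | Expected Poor at HD (of 10), at least | P(at least 9 of 10 Poor), at least |
|---|---|---|
| 0.70 | 7 | 0.15 |
| 0.90 | 9 | 0.74 |
| 0.95 | 9.5 | 0.91 |

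**Step 5: what the by-visit summaries leave out.**
SAP 3.4 gives the mean, 95% CI, SD, quartiles and range of the total at each visit, HD included. With complete data, the difference between two visit means equals the mean change. The SD of the change does not follow from the two visit SDs: SD²(change) = SD²(HD) + SD²(visit) − 2r·SD(HD)·SD(visit), and no planned table gives the within-patient correlation r. If a visit is missed, the two means come from different patients, because SAP 3.3 applies no imputation by default.

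**The case against.** The strongest reply is that little is lost. MMWS totals at HD and at every later visit will be tabulated with full statistics. The four components are tabulated by visit, so shifts inside Poor show up at component level across the group. Protocol 9.4.7 plans individual data listings, and with 10 patients each change can be worked out from them. The endpoint is descriptive, SAP 1.3.2.2 does not say that the comparison must be a numerical change, and a shift across the instrument's own categories is a legitimate comparison. All of this stands. It makes the gap small but does not close it: no planned output gives the within-patient change with its SD and CI, while the three neighbouring measures all have one.

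A reader might infer three stronger things that the documents do not support:

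- **That the shift table will in fact have a single starting row.** This needs motion and grip values at discharge, which are not given. Protocol 6.1.3 leaves the timing of discharge to the investigator. SAP 3.6 places the HD image within days of surgery, which makes low values plausible but not certain. At q = 0.70, the guaranteed probability of at least 9 of 10 Poor is only 0.15.
- **That a one-row table carries almost no information.** It would still show how many patients moved from Poor to Fair, Good or Excellent at each visit. It would be redundant with the category frequencies, not empty.
- **That the SAP breaks its own commitment.** The shift table is a comparison with HD. The issue is that it is coarse and out of line with the other measures.

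**Conclusion.** The point holds as an inconsistency with a modest consequence. It rests firmly on two things: the wording of SAP 4.3.3.2 set against 1.3.2.2, 3.5 and the neighbouring analysis sections, and the Appendix 4 arithmetic, under which motion and grip both below 50% give at most 60 points and are always Poor. The extent to which the shift table merely repeats the follow-up frequencies depends on an assumption about patients' state at discharge, for which only a range can be given (at least 7 to 9.5 of 10 expected to start as Poor if 70% to 95% are in that state).

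No safety result and no primary conclusion depends on this. What is missing is the paired change in one secondary clinical score. It is worth adding because the data are already collected and no planned table shows it.

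**What to change.** In SAP 4.3.3.2, extend the by-visit summary of the MMWS total to both the actual value and the change from HD, using the SAP 3.4 statistics as for grip strength and PRWE. Those statistics already report available and missing counts, so the number of patients with both values will be visible. Keep the component frequencies, the category frequencies and the shift tables as planned; removing or downgrading any of them gains nothing.

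The cost is one more column in an existing table, with no new data, visits or analysis set. If the SAP is already final, SAP section 1 provides the route: describe and justify the addition in the clinical study report.

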4.3.3.3 Numerical Rating Scale for Pain

Descriptive statistics will be provided at each visit for the actual value and change versus baseline (Screening) for the numerical rating scale for pain.

